inotrope score > 30; Vasoactive Inotrope score = dose of dopamine in $\mu\text{g}/\text{kg}/\text{min}$ + dose of dobutamine in $\mu\text{g}/\text{kg}/\text{min}$ + 100 X epinephrine dose in $\mu\text{g}/\text{kg}/\text{min}$ + 100 X norepinephrine dose in $\mu\text{g}/\text{kg}/\text{min}$ + 100 X phenylephrine dose in $\mu\text{g}/\text{kg}/\text{min}$ + 10000 x vasopressin dose in $\text{U}/\text{kg}/\text{min}$) two hours after initiation of study drug. Infusion will be continued until the OI decreases to < 7 (or OSI < 3.5 if no arterial blood gas is available). The study drug will be continued during surgery and if the patient requires either veno-arterial or veno-venous extracorporeal membrane oxygenation (VV-ECMO or VA-ECMO) if permitted by the clinical team. The maximum duration of study drug infusion is 72 h. After 70 h (if the patient is on 0.66 $\mu\text{g}/\text{kg}/\text{min}$ or 72h if the patient is on 0.33 $\mu\text{g}/\text{kg}/\text{min}$) of study drug infusion (or earlier if two consecutive OIs at least one hour apart are < 7 or OSIs < 3.5 if no arterial blood gas is available), the infusion rate of the study drug is weaned and subsequently discontinued. Data from a maximum of 4 echocardiograms, **if performed for clinical indications will be recorded**, (a) first echocardiogram, preferably prior to onset of study drug or within 6 hours of initiation of study drug, (b) second echocardiogram, 6 – 36 h after initiation of study medication (c) third echocardiogram, 36 h after initiation of study medication but prior to completion or discontinuation of study-drug and (d) first echocardiogram after completion of the study drug.

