2.2. SPECIFIC AIMS

Specific aim #1 - Efficacy: To determine the acute changes in oxygenation and echocardiography during treatment with IV milrinone (improvement in OI/OSI and PaO₂ at 24 hours from baseline and changes in right ventricular pressure and function at 24 – 72 h from baseline)

Specific aim #2 - Safety: To determine the safety of IV milrinone treatment by comparing the incidence of serious adverse events (severe hypotension, bleeding - intracranial and extracranial hemorrhage and arrhythmias).

Specific aim #3 - Outcome: To determine the infant's status (pulmonary and nutritional) at discharge and conduct a series of telephonic surveys at 4, 8 and 12 months of postnatal age to assess the impact of baseline characteristics (gender, gestational age at birth, mode of delivery, birth weight, time of diagnosis – antenatal vs. postnatal), study intervention and other therapies and interventions on infant's status.

Specific aim #4 - Feasibility: To derive preliminary estimates of the incidence of survival without ECMO in the control and IV milrinone treatment groups and to demonstrate the feasibility of conducting a large randomized controlled clinical trial.

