4.2. DETAILED STUDY PROCEDURES

For the purpose of the study, time period prior to study drug is defined as 12 hours prior to initiation to 30 minutes prior to initiation of study drug. Baseline is defined as the period 30 min prior to initiation of study drug. The monitoring period is defined as the period of study drug infusion and the first 24-hours following study drug cessation.

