- (ii) Diagnosed with severe or life-threatening renal dysfunction as defined in the MOP
- (iii) Diagnosed with severe or life-threatening arrhythmia as defined in the MOP not attributed to other causes such as electrolyte disturbances or a central line in the right atrium
- (iv) Diagnosed with severe or life-threatening intracranial bleed as defined in the MOP
- (v) Confirmed trisomy 13 or 18 by chromosomal analysis

Note: Respiratory deterioration is common in the natural history of CDH and should not be a reason for discontinuing study drug.

Duration of study intervention

In the absence of complications:

- (i) Milrinone/placebo is continued until oxygenation improves and two OIs obtained at least one hour apart are less than 7 (OSI < 3.5, if no arterial blood gas is available), then weaned according to the protocol below, or
- (ii) Milrinone/placebo is weaned and discontinued after a maximum of 3 days of therapy (72 hours from the initiation).

Surgery and ECMO:

- (i) Milrinone/placebo should preferably be continued if the patient requires ECMO irrespective of the mode of ECMO – VA vs. VV (Reason: although pharmacokinetics and volume of distribution are altered, milrinone may be beneficial with improved cardiac function especially during VV ECMO). (Note: ECMO use varies from center to center, but averages around 30%. This will mean that a fair number of the high risk patients are excluded unless they are enrolled soon after birth)
- (ii) It is recommended that the study drug be continued through surgery. If the surgical team prefers to discontinue the study drug, this indication should be recorded and study drug weaned as per protocol.

(iii) Note: if the clinical team decides to wean the baby off the study drug prior to ECMO or surgery, these reasons are documented as indications for discontinuing the study drug. It is not considered a protocol deviation or violation to wean the medication prior to surgery or ECMO. If serious, potentially drug-related complications occur, drug should be discontinued immediately (without weaning).

Study drug discontinuation criteria:

Milrinone/placebo is discontinued (without weaning) if the patient develops 'severe' or 'life-threatening' hypotension, intracranial or extracranial hemorrhage, renal dysfunction or arrhythmia that cannot be attributed to other causes.

Note:

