The study drug can be discontinued (with or without weaning) by the clinical team at any time point if the team is concerned that the study drug poses a risk to the infant. An indication for discontinuation should be recorded. The reason for discontinuation of study drug i.e., (a) due to completion of 72 h of infusion, (b) due to achievement of improved oxygenation (OI < 7 or OSI < 3.5, if no arterial blood gas is available), (c) secondary to occurrence of a side effect (intractable hypotension, intracranial hemorrhage, arrhythmia or renal dysfunction) or (d) due to a decision of the clinical team is recorded.

Weaning of study drug (figure 6):

(i) Once discontinuation criteria are reached, milrinone/placebo is weaned by 0.33 µg/kg/min every two hours and discontinued (total duration of wean 2 h if the patient is on 0.66 µg/kg/min and abrupt cessation of the medication infusion if the patient is on 0.33 µg/kg/min). If the subject is on 0.66 µg/kg/min, weaning is initiated at 70 hours after initiation of study drug. If the subject is on 0.33 µg/kg/min, no weaning is required and the study drug is stopped at 72 hours after initiation. NOTE: Once discontinuation criteria are reached and weaning is initiated, the study drug is discontinued after the wean. If the study drug is not weaned within 4 hours of meeting discontinuation criteria, this is considered a protocol deviation. If the wean was initiated following two OI values of < 7 (or OSI of < 3.5) and oxygenation worsens after initiating the wean, the study drug should still be discontinued as the end-point was met. However, open-label milrinone can be started soon after discontinuation of the study drug.

- (ii) If adverse events such as severe or life-threatening hypotension, intracranial or extracranial bleed,, arrhythmia or renal dysfunction are observed, study drug is abruptly stopped without gradual weaning.

Open-label milrinone use:

Immediately after completion of study intervention, open-label milrinone is permitted at the discretion of the clinical team. The study drug infusion will be 0.33 µg/kg/min at the time of cessation if gradual weaning protocol is adopted. It is recommended that the clinical team start open-label milrinone at this rate and adjust the dose based on clinical response. If the clinical team initiates open-label milrinone at 0.33 mcg/kg/min immediately after weaning the study drug, there is no discontinuity in therapy (for patients in the milrinone arm).

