5.1 SAMPLE SIZE AND POWER ESTIMATES

Sample Size: In the case series describing the effect of milrinone among neonates with CDH, baseline OI (mean \pm SD) was 10.6 ± 5.6 , and improved to 7.9 ± 6.2 and 5.1 ± 2.6 at 12-24 h and at 48-72 h, respectively (Patel 2012). Assuming that children receiving placebo will have no additional change in OI (mean change in OI = 0 at 24 hours), that children receiving milrinone will improve to a mean OI of 6.0 (a mean change in OI of 4.6) at 24 hours, and that the standard deviation of the change from baseline OI at 24 hours in each group is 6.2, 33 subjects in the control group and 33 subjects in the milrinone group would have 84% power to detect this difference with a two-sided alpha of 0.05 (note that 6.2 is a conservative standard deviation estimate, as data from the Patel et al study indicate that the standard deviation for change from baseline in OI at 24 hours may be as low as 1.5). Phrased differently, if both the control and treatment OI's were to change, for any given difference in OI, the sample size would be sufficient to detect an effect size of 0.7 with a power of 84%. The sample size will be sufficient to provide estimates of adverse event rates in the treatment group. The following table provides the 95% confidence intervals for observed adverse event rates varying from 6% to 49% for a sample size of 33 subjects.

Table 8. Confidence Intervals for Observed adverse event rates.

Point estimate	0.06	0.09	0.21	0.30	0.39	0.49
95% CI	(0.007, 0.2)	(0.02, 0.24)	(0.09, 0.39)	(0.16, 0.49)	(0.23, 0.59)	(0.31, 0.66)

Within the NRN centers, approximately 36% of neonates with CDH who are \geq 36 weeks PMA require ECMO. In a selective population (isolated CDH with OI \geq 10), we estimate that the risk of ECMO or death prior to discharge (or by day 120) will be approximately 40%. A sample size of 33 in the placebo arm would provide a 95% confidence interval for this estimate of (26%, 58%). The precision of estimates for outcome rates in the treatment group can be seen in table 8.

Limitations:

- (a) This study is not powered to compare rates of the outcome of death or ECMO between groups. To detect a reduction of 10% (from 40% incidence of death/ECMO in control arm to 30% incidence in the milrinone arm), with a 1:1 ratio of treatment and control subjects, a power of 0.8 and an alpha value of 0.05, we would require 376 subjects in each arm.

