5.5.1 Reporting Adverse Events

There is high morbidity and mortality associated with the natural course of CDH. The following measures will be used to monitor safety of the trial based on a review of adverse events. Adverse event reporting will be handled as follows:

- (i) **Potential Adverse Events** (as defined below) will be reported on the Adverse Events form.
- (ii) Because of the nature of the study population, mild events will not be recorded as adverse events unless they are also unexpected.
- (iii) Potential adverse events listed below that are severe, life-threatening or result in death (as per the MOP toxicity table) will be entered in the electronic data capture system (EDC) within 24 hours of discovery.
- (iv) **Serious Adverse Events** will be reported on the Adverse Events form, entered in the electronic data capture system (EDC) and reported to NICHD and the NRN data center within 24 hours of discovery (via SAE Narrative)
when:
 - a) they result in death **or**
 - b) they are possibly, probably or definitely related to the intervention **or**
 - c) they are unexpected. An unexpected event is defined as an adverse event not known to be associated with the natural course of CDH or a specified side-effect of interventions in the management of CDH.
- (v) All serious adverse events that meet one of the above criteria will be reviewed by the NICHD NRN Program Scientist (as medical monitor).
- (vi) All serious events that are marked as at least possibly related to the intervention will be forwarded to the Chair of the independent NRN DSMC for any further action.

The duration of reporting adverse events would include the period of administration of the study drug and 24 hours' post-infusion. This period will cover approximately 6 half-lives of milrinone and plasma levels are expected to be undetectable by 24 hours after completion of study-drug infusion.

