5.5.3 Interim Monitoring Plan and Stopping Rules

As mentioned previously, the DSMC will meet as per the following plan. A suggested schedule may include meeting after the first 10 subjects are enrolled and at 25% (~ 17 subjects), 50% (33 subjects), 75% (~ 50 subjects) of target sample size and after completion of enrollment.

In addition to monitoring trial progress, the DSMC will also review accumulating safety data for the trial. All safety data presented to the DSMC will be blinded to treatment group, though the report may be unmasked at the DSMC's request.

The three main adverse events that require close monitoring include severe hypotension , hemorrhage (intracranial and extracranial) and arrhythmia or death due to severe hypotension or intracranial hemorrhage or arrhythmia while on study drug infusion or 24 hours after cessation of study drug infusion.

The presence of the following adverse events *possibly, probably or definitely due to the study drug* in > 20% of subjects after enrollment of 33 patients with a statistically significant difference between the treatment arm and the placebo arm can lead to a discussion at DSMC regarding cessation of the trial.

- (a) Severe hypotension is defined by a decrease in mean blood pressure > 20 to 30 mmHg compared to baseline OR receiving extensive volume therapy (>40 to 80 ml/kg during a 24 hour period of the study monitoring period OR escalation of vasoactive inotropic score by >20 to 30 compared to baseline) The study monitoring period is the time on study drug therapy and within 24 hours of completion of study drug therapy.
- (b) Life-threatening hypotension - receiving volume therapy > 80 ml/kg during a 24 hour period of the study monitoring period OR escalation of vasoactive inotropic score by > 30 compared to baseline
- (c) Severe intracranial hemorrhage (unilateral or bilateral blood/ echodensity filling the ventricle(s) resulting in distension without parenchymal bleeding and without a midline shift) while on study drug therapy and within 24 hours of completion of study drug therapy.
- (d) Life-threatening intracranial hemorrhage - Parenchymal hemorrhage/ echodensity (including cerebellar hemorrhage) and / or any bleed/ echodensity associated with a midline shift.

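### Adverse events are counted over infusion plus 24 h, and infusion ends early on response, so the two arms may be observed for different lengths of time in the safety comparison

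*Combined protocol and SAP*

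**What the plan says.** The same response-dependent window appears in three places. Section 5.5.1: "The duration of reporting adverse events would include the period of administration of the study drug and 24 hours' post-infusion". Section 4.2: "The monitoring period is defined as the period of study drug infusion and the first 24-hours following study drug cessation". Section 5.5.3, for the main events the DSMC watches: "while on study drug infusion or 24 hours after cessation of study drug infusion".

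Infusion length is not fixed. Section 4.2.5: "Milrinone/placebo is continued until oxygenation improves and two OIs obtained at least one hour apart are less than 7", with an OSI equivalent of 3.5. Otherwise, as the opening summary puts it, "The maximum duration of study drug infusion is 72 h". The wean adds little: "total duration of wean 2 h if the patient is on 0.66" µg/kg/min, and none at the lower rate. Study drug is not restarted after a stop. It can also end for an adverse event, before surgery or ECMO, or by decision of the clinical team.

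Aim 2 (section 2.2) assesses safety by "comparing the incidence of serious adverse events" between arms. Section 5.4 assigns categorical outcomes to generalized linear models and mentions no common window, person-time or offset. After study drug stops, 4.2.5 provides for recording open-label milrinone, pressor and vasodilator use for 24 h only.

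**The concern.** The counting window is fixed by something that happens after randomization and that the trial hypothesises milrinone will change. The planning assumption in 5.1 is that "children receiving milrinone will improve to a mean OI of 6.0" at 24 h, already under the threshold of 7, while placebo stays at its baseline of 10.6. If that happened, more milrinone infants would leave observation early. Placebo infants would go on accumulating background events after the responders' windows had closed. Equal risks could then look like a benefit, and a modest excess on milrinone could look like no difference.

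The reason given in 5.5.1 for the 24 h tail is drug clearance. That supports an on-drug window, but it does not equalise follow-up between arms. Section 5.4 says all analysis is by intention to treat, and a window that closes on response does not fit that for safety.

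Grading can depend on the window too. In 3.5, severe extracranial bleeding is defined partly by red-cell volume transfused over the monitoring period, so a longer window gives more time to reach the volume.

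**Working it through.** **Plan's own figures.** Section 5.1: difference 4.6, SD 6.2, 33 per arm, two-sided alpha 0.05. The effect size is 4.6/6.2 = 0.742, and a two-sample t-test has power 84.3%, against 84% stated. Section 5.5.1: 24 h over the Table 4 half-life of 4.1 h is 24/4.1 = 5.9, against about 6 stated. Both reproduce.

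**Range of the window.** Longest: 72 + 24 = 96 h. Shortest: two qualifying OIs an hour apart soon after the start, plus any wean, plus 24 h, so little over 24 h.

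**Share stopping early.** I take the share with OI below 7 at 24 h as a stand-in for the share stopped early.

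- *Planning values:* means 6.0 and 10.6, with SD 6.2 (5.1 gives this for the case series at 12-24 h and reuses it as the SD of change). Normal tails: Φ((7 − 6.0)/6.2) = 0.564 for milrinone; Φ((7 − 10.6)/6.2) = 0.281 for placebo.
- *Assumed intermediate case:* baseline OI at least 10 with mean 15, change 0 or −4.6, SD 6.2. Simulation gives 0.347 v 0.147.
- *Table 6, infants with OI ≥ 10 at 6 h:* 20 ± 8 (n = 21) and 35 ± 19 (n = 36). The pooled mean is (21×20 + 36×35)/57 = 29.5 and the pooled SD 17.4. Simulation from a lognormal cut at OI 10, with the same changes, gives 0.094 v 0.033.

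**Recorded risk.** Assume the same true risk in both arms, 30% over 96 h. Early stoppers are given a 48 h window (stop at 24 h plus 24 h) and everyone else 96 h.

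- Constant hazard: risk by 48 h = 1 − 0.70^(48/96) = 16.3%.
- Front-loaded (half the cumulative hazard in the first 24 h): fraction by 48 h = 0.5 + 0.5×(24/72) = 0.667, so risk = 1 − 0.70^0.667 = 21.2%.
- Recorded incidence = share × short-window risk + (1 − share) × 30%.

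For example, with planning values and constant hazard: milrinone 0.564×16.3 + 0.436×30 = 22.3%; placebo 0.281×16.3 + 0.719×30 = 26.2%.

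| OI values | Stopped early (milrinone v placebo) | Constant hazard | Front-loaded |
|---|---|---|---|
| Planning (5.1) | 56% v 28% | 22.3% v 26.2% (gap 3.9) | 25.0% v 27.5% (gap 2.5) |
| Assumed mean 15 | 35% v 15% | 25.3% v 28.0% (gap 2.7) | 26.9% v 28.7% (gap 1.8) |
| Like Table 6 | 9% v 3% | 28.7% v 29.5% (gap 0.8) | 29.2% v 29.7% (gap 0.5) |

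True risks are equal throughout, so every gap comes from the window alone. Over a fixed 0-96 h window all six gaps are zero.

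**Scale.** A gap of 3.9 points is 0.039×33 = 1.3 infants. The 95% interval for a difference near 25% with 33 per arm is about ±1.96×√(2×0.25×0.75/33) = ±21 points.

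**The case against.** **The planning values fit the trial badly.** A normal OI with mean 6.0 and SD 6.2 puts about 17% of infants below zero. A baseline of 10.6 ± 5.6 puts about 46% below the entry threshold of 10. Table 6 is closer to the eligible population and gives a gap under 1 point. This stands, and the planning case should be read as the upper end of the three shown.

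**Hypotension comes early.** The exclusion criteria (4.1.2) describe hypotension risk as high in the first 24 h of infusion, and every surviving infant is observed for at least that long. This stands: hypotension is the least exposed event, and the front-loaded column suits it better.

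**Intracranial bleeding is scanned for in every infant.** A second ultrasound follows completion of study drug, so detection depends less on infusion length. This largely stands. However, the scan may come up to 96 h after completion, while 5.5.3 counts severe intracranial hemorrhage only to 24 h and gives no time limit in its life-threatening item. Those passages need reconciling.

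**The direction is not certain.** Stops for ECMO, surgery, adverse events or clinician choice also shorten the window. If milrinone works, ECMO-related stops may fall more on placebo. This stands.

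**A fixed window has its own bias.** It includes open-label milrinone in both arms, which can dilute a real drug effect. This stands as the cost of the fix and is why the present window is worth keeping as a supplement.

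**Stronger readings.** A reader might infer a larger gap by giving early stoppers a 36 h window. That pairs the share below 7 at 24 h with a stop at 12 h, and the documents do not support the pairing. A reader might also take the 80-90% vasoactive use in 3.5 as a background rate of severe hypotension, or suppose that placebo infants are watched through surgery. The first figure is any vasoactive treatment with no timing, and no section places surgery within 96 h.

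**Conclusion.** The design feature is real: follow-up for adverse events depends on response, may differ systematically between arms, and is not adjusted for in 5.4. If milrinone improves oxygenation, crude incidence would tend to favour it, subject to the offsetting stops above. The gap runs from about 4 points (planning OI values, constant hazard) to under 1 point (OI values like Table 6), or about one infant in 33 at most. These figures rest on an assumed 30% risk over 96 h, an assumed 48 h window for early stoppers, assumed hazard shapes, and OI at 24 h standing in for the stopping rule.

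The concern is greatest for later arrhythmia and extracranial bleeding and least for hypotension. Death and ECMO are followed to discharge or day 120 and are unaffected. It would go too far to infer that the safety comparison is invalid or that DSMC oversight fails. The 5.5.3 trigger counts only events judged at least possibly drug-related, leads to a discussion rather than an automatic stop, and the DSMC may ask for unmasked reports. The change is still worth making: the remedy is cheap, and the pilot's data are meant to inform a definitive trial of 752 infants.

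**What to change.** - In 4.2, 5.4 and 5.5.1, define the between-arm safety comparison as the listed events over a fixed 0-96 h from study-drug initiation in every infant, whatever the stop time. This is the longest window the present rule allows.
- In 4.2.5, extend recording of pressor, vasodilator and open-label milrinone use from 24 h after cessation to 96 h from initiation. Without this, hypotension cannot be scored for early stoppers.
- State how transfusion and fluid volumes are accumulated for the fixed-window table.
- Keep infusion plus 24 h as an on-treatment supplement, with hours observed and open-label milrinone use reported by arm.
- Show the DSMC both tables alongside the existing 5.5.3 trigger for drug-related events.

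No dosing or study-drug stopping rule changes. The cost is protocol and case-report-form wording, a few more days of chart abstraction for infants who stop early, and some dilution from open-label milrinone in the fixed window, which the supplement makes visible.

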Infusion of the study drug will be stopped if the mean blood pressure decreases < 35 mmHg and by > 20 mmHg (from pre-study drug mean blood pressure) after initiation of study drug and remains low for 2 hours despite treatment with > 40 ml/kg/24h of fluids and vasoactive medications (with a vasoactive inotrope score of > 30). Once the study drug is discontinued for improvement in oxygenation or a decrease in systemic blood pressure, it will not be restarted even if the condition leading to discontinuation changes (such as change in oxygenation or blood pressure). However, clinical providers can initiate open-label milrinone at their discretion. Study drug will also be stopped in the presence of renal dysfunction and/or development of a large intracranial (intraventricular with distension of the ventricle or parenchymal) bleed/echodensity.

Primary Outcome:

The primary outcome is the oxygenation response, as determined by change in OI (or OSI if no arterial blood gas is available) at 24h after initiation of study drug. In patients that require ECMO or die prior to completion of 24h from the initiation of the study drug, the last OI (or OSI if no arterial blood gas is available) prior to initiation of ECMO or death will be used for analysis. In patients without an arterial line (or if the line is lost), oxygen saturation index (OSI) will be calculated using a preductal oximeter. (Rawat, Chandrasekharan et al. 2015)

Secondary outcomes:

- (i) Oxygenation response at 24 h after initiation of study drug assigning a minimum OI of 40 or OSI of 20 for subjects that need ECMO or die after initiation of study drug infusion but prior to 24h of study-drug infusion. In this analysis if the patient's OI is 30 (or OSI of 15) and is cannulated for ECMO due to hemodynamic instability, he/she will be assigned an OI of 40 (or OSI of 20). However, if the OI prior to ECMO is 47 (i.e., > 40), the higher number (47) will be used for analysis of this secondary outcome.
- (ii) Oxygenation index at 48 and 72 h after initiation of study drug (or OI/OSI at the time of initiation of ECMO or immediately prior to death, for infants placed on ECMO or died before these time points),

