 - Midline shift secondary to mass effect from an intracranial hemorrhage
- thrombocytopenia (platelet count < 80,000/mm³) despite blood product administration on the most recent blood draw prior to randomization
- coagulopathy (PT INR > 1.7) despite blood product administration on the most recent blood draw (if checked – there is no reason to check PT for the purpose of this study)
- aneuploidy associated with short life span (such as trisomy 13 or 18) will not be included in the study (infants with trisomy 21 can be included in the study)

- use of milrinone infusion prior to randomization (the use of other inhaled pulmonary vasodilators such as iNO, inhaled epoprosternal, inhaled Treprostinal, inhaled PGE1 and oral such as endothelin receptor antagonists is permitted – Note: it is unlikely to be on oral pulmonary vasodilators early in the course of CDH)
- ongoing therapy with parenteral (intravenous or subcutaneous) pulmonary vasodilators such as IV/SQ prostacyclin analogs (Epoprostenol – Flolan® or Treprostinal – Remodulin®) or IV phosphodiesterase 5 inhibitors (sildenafil – Revatio®) at the time of randomization. Administration of IPGE1 is not an exclusion criteria. In addition, initiation of therapy with these two classes of parenteral medications (except IPGE1) during the first 24 hours of study drug initiation is not permitted and will be considered a protocol deviation. The risk of systemic hypotension is high during the first 24 hours of study-drug (milrinone) infusion and hence parenteral administration of other pulmonary vasodilators is avoided to minimize risk of hypotension.
- Subjects already on ECMO or patients who are being actively considered for ECMO by the neonatal or surgical team
- Infants with hypoxic-ischemic encephalopathy (HIE) undergoing therapeutic hypothermia
- attending (neonatal, critical care or surgical) refusal for participation in the trial (including concern about presence of hemodynamic instability)

Note:

1. A clotting profile evaluation is not required prior to enrollment. However, a cranial ultrasound (covered by the study budget) must be obtained either prior to initiation of study drug or within 4 hours of initiation of study drug. Not obtaining a cranial ultrasound within this time period will be considered a protocol deviation.

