Criteria for re-initiation of study drug:

After the patient has met criteria for study drug discontinuation once (due to improvement in oxygenation and meeting OI criteria, or due to side effects such as severe hypotension, intracranial bleeding or renal dysfunction), study drug is discontinued and cannot be reinitiated even if the indication for initial discontinuation is resolved (for e.g., OI exceeds 10 after cessation of study drug or hypotension is resolved and blood pressure is normal etc.,). The clinical team may start open-label milrinone.

During the post-study drug infusion period, data regarding open-label milrinone use, pressor use, and vasodilator use will be recorded for 24 hours after cessation of study-drug.

Fluid intake:

- (i) As systemic hypotension and fluid bolus administration are common in patients with CDH and PPHN, it is important to record daily fluid intake.
- (ii) Total fluid intake (including maintenance fluids/TPN, flushes, medications, boluses and blood products) will be recorded for three 24-hour periods as entered in the nursing notes/EMR (please see MOP for details).

Clinical criteria for ECMO:

The decision to place an infant with CDH on ECMO is ***entirely up to the clinical team***. Many centers prefer to use ECMO for preoperative stabilization. The following general guidelines are provided as criteria for ECMO (Reiss, Schaible et al. 2010) (Snoek, Reiss et al. 2016):

- (i) Oxygenation index is consistently ≥ 40 for at least 3 h and/or
- (ii) Inability to maintain preductal saturations $> 85\%$ or postductal saturations $> 70\%$ and/or
- (iii) Increased PaCO_2 and respiratory acidosis with $\text{pH} < 7.15$ despite optimization of ventilator management and/or
- (iv) $\text{PIP} > 28 \text{ cm H}_2\text{O}$ or mean airway pressure $> 17 \text{ cm H}_2\text{O}$ is required to achieve saturations $> 85\%$ and $\text{PaCO}_2 < 65 \text{ mmHg}$ and/or
- (v) Inadequate oxygen delivery with metabolic acidosis as measured by elevated lactate $\geq 5 \text{ mM/L}$ and $\text{pH} < 7.15$ and/or
- (vi) Systemic hypotension (mean blood pressure $< 30 \text{ mmHg}$), resistant to fluid and inotropic support, resulting in hypoperfusion and/or oliguria (urine output $< 0.5 \text{ mL/kg/h}$) for at least 12-24h

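### The 24 h post-infusion adverse event window is treated as washout, but open-label milrinone may start in it, so counting by randomised arm can dilute the Aim 2 safety comparison, chiefly for hypotension

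*Combined protocol and SAP*

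**What the plan says.** Section 5.5.1 fixes the reporting period: "The duration of reporting adverse events would include the period of administration of the study drug and 24 hours" after infusion. Its reason is washout: "This period will cover approximately 6 half-lives of milrinone", and "plasma levels are expected to be undetectable by 24 hours after completion of study-drug infusion". Section 5.5.3 uses the same window in its adverse event definitions: "The study monitoring period is the time on study drug therapy and within 24 hours of completion of study drug therapy".

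Section 4.2.5 (Open-label milrinone use) states: "Immediately after completion of study intervention, open-label milrinone is permitted at the discretion of the clinical team". The synopsis, after describing early discontinuation for improved oxygenation or a fall in blood pressure, adds: "However, clinical providers can initiate open-label milrinone at their discretion". Section 4.2.5 also notes that an immediate start leaves therapy unbroken, but only for infants in the milrinone arm.

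On early exposure, section 4.1.2 says: "The risk of systemic hypotension is high during the first 24 hours of study-drug (milrinone) infusion".

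Section 2.2 (Aim 2) compares the incidence of serious adverse events: severe hypotension, bleeding and arrhythmias. Section 5.4 puts every analysis on an intention-to-treat basis. Section 4.2.5 provides that "data regarding open-label milrinone use, pressor use, and vasodilator use will be recorded for 24 hours after cessation of study-drug", but section 5.4 plans no safety analysis that uses this information.

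**The concern.** The washout argument holds only if no milrinone is given in the 24 h tail. Where open-label drug starts, the tail is active exposure, and what it means differs by arm. A milrinone-arm infant who continues has usually passed the early period of exposure. A placebo infant enters it for the first time, and the tail is as long as the period that section 4.1.2 describes as high-risk for hypotension. Hypotension caused by milrinone in that infant is counted under placebo.

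This shrinks the between-arm difference. The safety hypothesis in section 2.1 is that milrinone will not increase these risks, so the dilution runs toward the hoped-for answer. Safety is one of the stated reasons for the pilot, whose results are to inform the definitive trial.

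**Working it through.** **The plan's own figure.** Table 4 gives a half-life of 4.1 ± 1.1 h in neonates with PPHN. 24 / 4.1 = 5.85 half-lives, leaving 0.5^5.85 = 1.7% of the drug; over ±1 SD the range is 24 / 5.2 = 4.6 to 24 / 3.0 = 8.0 half-lives. The figure of about 6 reproduces, for infants given no further milrinone.

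**Dilution model.** Let p0 be the event risk without milrinone, pm the risk in the milrinone arm, f the share of placebo infants who start open-label milrinone in the tail, and g the share of the excess risk (pm − p0) that falls in those open-label hours. Then:

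- observed placebo risk q = p0 + f × g × (pm − p0)
- observed difference = (pm − p0) × (1 − f × g)

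**Inputs.**

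- n = 33 per arm, from section 5.1.
- f is not in the documents. I use 0.17 (background use in the network, section 2.3.3 and Table 9), 0.30 (background use in a children's hospital database, synopsis) and 0.50 as a high case. None of these measures first starts after study drug.
- p0, pm and g are assumptions. g = 1 is the upper bound; g = 0.5 is a milder case.

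**Example.** With p0 = 0.10, pm = 0.40, f = 0.30 and g = 1, q = 0.10 + 0.30 × 1 × 0.30 = 0.19, and the difference is 21 points instead of 30. With g = 0.5, q = 0.145 and the difference is 25.5 points.

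**Results.** Power is for Fisher's exact test, two-sided 0.05, 33 per arm, by enumeration of both binomials. Each range runs from g = 1 to g = 0.5.

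| Assumed risks | f = 0 | f = 0.17 | f = 0.30 | f = 0.50 |
|---|---|---|---|---|
| 10% vs 40%: difference (points) | 30 | 24.9–27.5 | 21–25.5 | 15–22.5 |
| 10% vs 40%: power | 75% | 52–64% | 36–55% | 18–42% |
| 10% vs 30%: difference (points) | 20 | 16.6–18.3 | 14–17 | 10–15 |
| 10% vs 30%: power | 42% | 27–34% | 18–29% | 9–21% |

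A higher background risk gives the same pattern: at 20% vs 50%, power falls from 66% to 48–57%, 35–50% and 19–39%.

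**The case against.** Several points on the other side stand.

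- **Size.** A reader might take the lower end of each range as the estimate. It is an upper bound on the loss: it gives each crossing placebo infant, in at most 24 h of open-label drug, the whole excess risk of an infusion of up to 72 h plus its tail. Section 4.2.5 recommends that open-label drug start at 0.33 µg/kg/min, whereas study drug may be raised to 0.66, and some infants would start late in the tail. The 17% and 30% describe background use; the true share could be higher, or close to zero.
- **Reach.** A reader might extend the early-risk argument to bleeding and arrhythmia. The documents describe the first 24 h as high-risk for hypotension only.
- **DSMC guideline.** A reader might infer that the trigger in section 5.5.3 is biased in the same way. It counts only events judged at least possibly due to study drug, so events after open-label milrinone may be attributed elsewhere and left out. Any that do count would raise the limb requiring events in more than 20% of subjects. The trigger applies after 33 infants in total, so power at 33 per arm does not measure it, and it leads only to a discussion.
- **Existing protection.** Section 4.2.5 expects no open-label milrinone during study drug, so the randomised infusion period is free of this crossover. Section 5.4 models vasoactive inotrope score with a time-by-treatment term. The treatment-arm event rates promised in section 5.1 are not affected by placebo crossover.
- **Intention to treat.** Counting by randomised arm is a legitimate treatment-policy comparison. Censoring at open-label start would shorten follow-up unequally and could lower the placebo count. The follow-up cranial ultrasound may come up to 96 h after study drug, so a bleed first seen there may not be datable to before or after open-label start.

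These points limit the size and shape the remedy. They do not restore the washout rationale for infants who receive open-label milrinone, or supply the missing split.

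**Conclusion.** The concern holds in a limited form. As written, the plan can count milrinone-caused hypotension under placebo and so dilute the Aim 2 comparison toward no harm. The direction follows from the documents, given some placebo crossover and a hypotensive effect of milrinone; the size does not. If no placebo infant starts open-label milrinone in the window, there is no effect. Under the assumed risks, the share of the true difference kept is 1 − f × g: 83–91% at f = 0.17, 70–85% at 0.30 and 50–75% at 0.50. In a trial with 33 per arm, the resulting power loss could matter.

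The documents do not support reading this as an established bias in the DSMC trigger, as early excess risk for bleeding or arrhythmia, or as grounds for replacing the intention-to-treat count.

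**What to change.** Keep the full infusion-plus-24 h intention-to-treat count as the main safety comparison. Then:

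1. In section 5.4 and the DSMC tables, pre-specify a supplementary tabulation by arm of (a) events before any open-label milrinone, with time at risk shown or as rates per time at risk, and (b) events after open-label milrinone starts.
2. Show separately, as undatable, intracranial bleeds first seen on the post-infusion ultrasound in infants who received open-label milrinone.
3. Confirm that open-label start times are captured. Section 4.2.5 already records use over these 24 h, and section 3.2 (vi) foresees initiation times for individual inotropes and vasodilators.
4. In section 5.5.1, limit the washout rationale to infants not given open-label milrinone.

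The cost is SAP and table wording and, at most, one start-time field. The downside is that the supplementary comparison is open to informative censoring and unequal follow-up, which is why it sits beside the main count and does not replace it. No change to dosing or to access to open-label milrinone is proposed.
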